4.2 Exclusion Criteria

A subject will be excluded from this study if he/she meets any of the following criteria:

1. Subjects diagnosed with acute promyelocytic leukemia
2. Concomitant therapy that includes other chemotherapy that is or may be active against AML, except for prophylaxis and/or treatment of opportunistic or other infection with antibiotics, antifungals, and/or antiviral agents
3. Prior mediastinal radiotherapy
4. Any condition that, in the opinion of the Investigator, places the subject at unacceptable risk if he/she were to participate in the study
5. LVEF <50%, valvular heart disease, or severe hypertension (see [Table 1](#)). Cardiac subjects with a New York Heart Association classification of 3 or 4 will be excluded. (Cardiology consultation should be requested if any question arises about cardiac function.) This also includes subjects with baseline QT/QTc interval >480 msec, a history of additional risk factors for torsade des pointes (e.g., heart failure, hypokalemia, family history of Long QT Syndrome), and use of concomitant medications that significantly prolong the QT/QTc interval.
6. Clinically relevant serious comorbid medical conditions including, but not limited to, active infection, recent (less than or equal to 6 months) myocardial infarction, unstable angina, symptomatic congestive heart failure, uncontrolled hypertension, uncontrolled cardiac arrhythmias, chronic obstructive or chronic restrictive pulmonary disease, active CNS disease uncontrolled by standard of care, known positive status for human immunodeficiency virus and/or active hepatitis B or C, cirrhosis, or psychiatric illness/social situations that would limit compliance with study requirements
7. Pregnant, lactating, or not using adequate contraception
8. Known allergy to anthracyclines
9. Any evidence of mucositis/stomatitis or previous history of severe (\geq Grade 3) mucositis from prior therapy
10. Required use of strong inhibitors and inducers of the Cytochrome P450 family of enzymes (CYP) and transporters that cannot be held during treatment days

4.3 Subject Withdrawal

Subjects may voluntarily withdraw from the study at any time for any reason and without prejudice to further treatment or the Investigator may withdraw subjects if necessary.

Subjects who are removed from the study will undergo all study evaluations described for the End of Study visit ([Section 6.4](#)). The reasons for withdrawal will be recorded.

The reasons for which a subject may be prematurely discontinued include the following:

1. Subject has unacceptable toxicity, subject demonstrates manifestations of cardiotoxicity, or subject has >10% decrease in ejection fraction based on scans. All subjects who are discontinued as a result of an adverse event should be followed for as long as necessary to document the resolution or stabilization of the event.
2. Subjects with disease progression
3. Subject withdrawal of consent
4. Investigator's discretion
5. General or specific changes in the subject's condition that renders the subject ineligible for further treatment
6. If pregnancy occurs or is suspected during study drug treatment, amnomycin must be discontinued immediately. The subject should be referred to an obstetrician/gynecologist experienced in reproductive toxicity for further evaluation and counseling. If none is immediately available, contact Moleculin Biotech for a referral.
7. If the subject's continued participation poses unacceptable risk for any other reason or if they are not compliant with the study

4.3.1 Withdrawal Procedures

Subjects withdrawn from the study will complete the end of study (EOS) procedures described in [Section 6.4](#) and be followed until resolution of any AEs or until the unresolved AEs are judged by the Investigator to have stabilized.

The Investigator will promptly notify the Medical Monitor of a subject's withdrawal for reasons related to toxicity.

4.3.2 Subject Replacement

Subjects withdrawing in the cohort dose-escalation period for reasons other than toxicity who have not taken all 3 doses during the induction cycle and/or fail to complete restaging after completion of the treatment cycle such that safety is not evaluable will be replaced. However, subjects experiencing a DLT in the dose-finding cycle will not be replaced.

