3.3 Safety Considerations

Subjects will be hospitalized for the full 3 days of liposomal annamycin administration. If a subject experiences a DLT as defined in [Section 3.4](#), or any severe or life-threatening event occurs at any time over the first 3 days, dosing should be stopped and the subject should be permanently discontinued from the study. In addition to the DLT criteria in [Section 3.4](#), the severe or life-threatening events include (but are not limited to) development of an anaphylactic reaction during or after the infusion, clinical or radiological evidence of left ventricular dysfunction with dyspnea and pulmonary rales, cardiomegaly or signs of pulmonary hypertension on chest x-ray, or acute cardiotoxicity ([Section 3.3.1](#)).

Additional criteria for safety evaluation after the initial dose during the induction cycle includes creatinine levels increasing to 1.5 times those of baseline or liver function tests increasing to 2 times those of baseline, in which case the next dose of the study drug will be decreased by 25%. If there is further deterioration of organ function after the next dose, the subject will be permanently discontinued from the trial. If these changes are acutely 2 or 3 times those of baseline, respectively, the study drug will be held, and subjects will be monitored for resolution of these changes. If there is prompt resolution (within 2 to 5 days), a rechallenge at a 25% lower dose will be attempted, and if any additional toxicity is observed, the subject will be permanently

discontinued from the trial. If resolution takes longer than 5 days, the subject will not be rechallenged and will be permanently discontinued from the trial.

Subjects successfully completing the first 3 days of dosing will then be evaluated weekly thereafter during the induction cycle of treatment (the induction cycle consists of 21 days [3 weeks total], with the first 3 consecutive days of daily liposomal annamycin treatment followed by 18 days off of liposomal annamycin).

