3.4 Criteria for Dose-Limiting Toxicity

A DLT is defined as any of the following clinically significant AEs or laboratory abnormalities that occur during the DLT evaluation period except those that are clearly and incontrovertibly due to extraneous causes, including disease progression, underlying disease, concurrent illness or concomitant medications. The DLT evaluation period is defined as the first day of treatment (Day 1) until Day 28. DLT observation periods for safety monitoring in expansion cohorts will be as above. The severity of AEs will be graded according to the NCI CTCAE v5.

Any Grade ≥ 3 nonhematologic or extramedullary toxicity with the following exceptions:

- Anorexia or fatigue;
- Grade 3 nausea and/or vomiting if not requiring tube feeding or total parenteral nutrition or diarrhea if not requiring or prolonging hospitalization that can be managed to Grade ≤ 2 with standard antiemetic or antidiarrheal medications used at prescribed dose within 7 days of onset;
- Grade 3 mucositis that resolves to Grade ≤ 2 within 7 days of onset;
- Grade 3 fever with neutropenia, with or without infection; or
- Grade 3 infection.

Any subject demonstrating the defining criteria for Hy's Law ([Appendix D](#)) will be discontinued from the study, and this will be considered a DLT.

Subjects who do not achieve a remission of leukemia will not be evaluable for hematological toxicity.

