4. ECG

6.3 On-Study Evaluations

6.3.1 Study Drug Administration

Dosing will be in the morning at approximately the same time each day. Subjects will be treated with a daily 2-hour intravenous infusion of liposomal annamycin for 3 consecutive days. Prophylaxis as described in [Section 3.6](#) will be administered. Antiallergic premedication with diphenhydramine at a dose of 50 mg administered intravenously must be administered before each dose of liposomal annamycin. During each period of study drug administration subjects must be observed for at least 4 to 6 hours following daily liposomal annamycin administration. The following evaluations will be conducted during the 3 days of liposomal annamycin administration (Days 1 to 3):

1. Physical examination including weight, vital signs, and oral examination on Days 2 and 3
2. Blood samples for pharmacokinetic analysis collected at predose and at 0.25, 0.5, 1, 2, 4, 8, and 24 hours after the start of liposomal annamycin infusion on Day 1 and Day 3 for 3 subjects at each dose and 6 subjects at the RP2D who complete the 3 days of dosing
3. Blood samples for cardiac biomarkers (troponin-I and troponin-T) collected at predose, at the end of infusion on Day 3, and on Day 21
4. ECG monitoring at predose and at 4 hours and 24 hours after the start of liposomal annamycin infusion on Day 1, Day 2, and Day 3 for all subjects at each dose and 6 subjects on Day 1 and Day 3 only at the RP2D who complete the 3 days of dosing, coinciding with pharmacokinetic (PK) evaluations
5. Monitoring of adverse events and review of concomitant medications and concurrent illnesses (treatment-emergent or worsening illness must be recorded as an adverse event). Evaluation of blood chemistries and blood counts daily. Over the 3 days of initial dosing, if any toxicity occurs, including blood count abnormalities, dosing should be interrupted until resolution, with rechallenge at a 25% lower dose, based on guidelines in [Sections 3.3](#) and [3.4](#). If any DLT is encountered (as defined in [Sections 3.3](#) and [3.4](#)) including any severe or life-threatening event, the subject should be discontinued from the study. These specific events include (but are not limited to) development of an anaphylactic reaction during or after the infusion or clinical or radiological evidence of left ventricular dysfunction with dyspnea and pulmonary rales, cardiomegaly, or signs of pulmonary hypertension on chest x-ray.
6. Concomitant medications

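### Sections 3.1, 3.3, 3.4 and 6.3.1 do not agree on what a DLT is or what triggers a dose cut, and the count of reduced or stopped subjects toward the MTD is only implied

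*Combined protocol and SAP*

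**What the plan says.** **What sets the MTD.** Sections 3.1 and 3.2 take the highest level with fewer than 2 DLTs among up to 6 subjects. Neither sets a condition on dose received.

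**What a DLT is.**
- Section 3.1 describes a Grade 3 or higher toxicity that is definitely due to the drug and either irreversible or beyond medical management. It points to Section 3.4 for further definition.
- Section 3.4 counts Grade 3 or higher "nonhematologic or extramedullary toxicity with the following exceptions" (a short list follows) and Hy's Law cases. It leaves out only events that plainly and beyond dispute have another cause.
- Section 3.3 introduces its severe or life-threatening events with "In addition to the DLT criteria in" Section 3.4.
- Section 6.3.1 takes DLTs to be defined in both 3.3 and 3.4, "including any severe or life-threatening event, the subject should be discontinued from the study".

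**What triggers a cut, hold or stop.** In Section 3.3, when creatinine reaches 1.5 times or liver tests 2 times the subject's own baseline, "the next dose of the study drug will be decreased by 25" percent. Then: "If there is further deterioration of organ function after the next dose, the subject will be permanently discontinued from the trial". At an acute 2 or 3 times baseline, respectively, the drug is held. Recovery within 2 to 5 days leads to rechallenge at a 25% lower dose. "If resolution takes longer than 5 days, the subject will not be rechallenged" and leaves the trial. Section 6.3.1 says instead that, over the dosing days, "if any toxicity occurs, including blood count abnormalities, dosing should be interrupted until resolution, with rechallenge at a 25% lower dose, based on guidelines in"; the sections it names are 3.3 and 3.4.

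**Who is replaced.** Section 4.3.2 replaces "Subjects withdrawing in the cohort dose-escalation period for reasons other than toxicity who have not taken all 3 doses during the induction cycle", or who miss restaging, if safety is then not evaluable. DLT subjects are not replaced. Section 3.1 allows replacement only when the stop was not due to a drug-related adverse event.

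**The concern.** The DLT count is the only formal rule behind the MTD, and the count is small. If two sections classify the same event differently, two sites or two meetings of the Safety Review Committee/Consultant (SRC) can reach opposite conclusions from the same data. Identifying the RP2D is part of the primary objective, and up to 21 further subjects are then enrolled at the MTD or RP2D.

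A second, smaller issue is exposure. Section 3.3 produces subjects who are reduced or stopped for renal or hepatic changes without necessarily having a DLT. They can support calling a level tolerated without having received that level in full, and no sentence says so expressly.

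**Working it through.** **1. The plan's own figures.** Two levels × 6 subjects = 12, and 12 + 21 = 33. Both match Section 3.1. The plan gives no expected DLT rate and no operating characteristics for the 3+3, so there is no probability to reproduce.

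**2. The sections side by side.**

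| Event | One reading | Another reading |
|---|---|---|
| Grade 3 nonhematologic event, not on the exception list, reversible, only possibly drug-related | 3.1: not a DLT | 3.4: DLT |
| Listed severe event with no grade attached (e.g. cardiomegaly on chest x-ray), if below Grade 3 | 3.3: stop, listed beside the DLT criteria | 6.3.1: DLT |
| Acute creatinine or liver-test rise that reaches Grade 3 or higher | 3.3: hold, possible rechallenge, no upper limit on the rise | 3.4: DLT, hence permanent stop under 3.3 |
| Creatinine 1.5 times or liver tests 2 times baseline | 3.3: next dose cut, no hold | 6.3.1: interrupt until resolved, then rechallenge lower |
| Blood count abnormality in the dosing days | 3.3: no trigger; 3.4: no criterion (its one hematologic sentence is about evaluability) | 6.3.1: interrupt, citing 3.3 and 3.4 |

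The first three rows can change the DLT count. The last two change the dose received.

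**3. Effect of one reclassified event.**
- No other DLT in the first 3: 0/3 (escalate) becomes 1/3 (expand to 6).
- One other DLT in the first 3: 1/3 (expand) becomes 2/3 (already not tolerated).
- One other DLT in 6: 1/6 (tolerated) becomes 2/6 (not tolerated).

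**4. The implied count.** A subject stopped for drug-related toxicity below a DLT falls outside both replacement clauses (4.3.2 and 3.1). A subject who is cut but completes dosing has not withdrawn. The MTD rule counts only DLTs and has no exposure condition. Both subjects therefore stay at the assigned level as non-DLTs.

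Such subjects can exist. A transaminase rising from 0.5 to 1.5 times the upper limit of normal has tripled, which meets the Section 3.3 hold. Yet it is inside the entry limit (below 3 times, Section 4.1) and below the Appendix D threshold (3 times). The documents do not reproduce the CTCAE grade limits, so the entry limit serves here as the marker that this value is not severe.

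**5. Exposure at Level 2.** Planned: 3 × 120 = 360 mg/m². A cut dose is 0.75 × 120 = 90.
- One dose cut: 120 + 120 + 90 = 330 (92%)
- Doses 2 and 3 cut: 120 + 90 + 90 = 300 (83%), equal to Level 1's 3 × 100
- Dose 2 cut, then stopped: 120 + 90 = 210 (58%), below Level -1's 3 × 90 = 270
- Held after dose 1 and not resumed: 120 (33%)

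**6. Illustration only; every input is assumed.** Let p be the average DLT risk per subject and q = 1 − p. Then P(level clears) = q³ + 3pq² × q³. If a share s is reduced and keeps a fraction r of the full-dose risk f, p = f(1 − s) + f·r·s.

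| f | s = 0 | s = 10%, r = 0.5 | s = 1/3, r = 0.5 | s = 10%, r = 0.75 | s = 1/3, r = 0.75 |
|---|---|---|---|---|---|
| 20% | 71% | 73% | 78% | 72% | 74% |
| 30% | 49% | 53% | 60% | 51% | 55% |
| 40% | 31% | 34% | 43% | 33% | 37% |

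Example: f = 30%, s = 10%, r = 0.5 gives p = 0.285 and 0.715³ + 3(0.285)(0.715)⁵ = 0.525. With r = 1 nothing changes. At 10% reduced the shift is about 3 points at most.

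**The case against.** **Section 3.4 governs.** Section 3.1 refers to 3.4 for detail, and 3.2 cites 3.4 as the definition. That is the natural reading, but it does not remove the conflict. Section 3.1 adds conditions (definite attribution, irreversibility or unmanageability) that 3.4 lacks. The synopsis repeats most of them without any pointer to 3.4.

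**The listed severe events would be Grade 3 or higher anyway.** Many probably would. Some entries are radiological signs with no grade attached, so 3.4 does not settle them.

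**The cut and hold triggers are clinical management, not counting.** This is largely true. They matter here because they decide how much of the assigned dose a counted subject received.

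**The SRC covers it.** It approves escalation and designates DLTs (8.2), and it adjudicates safety and disposition (8.1). Escalation also requires the absence of safety concerns (3.1). The RP2D rests on aggregate data (3.1, 3.2), DLT observation continues in expansion (3.4), and the Medical Monitor and SRC review all data continually (Section 10). This stands and limits the consequence. But the SRC may be a single consultant, and the text it would apply is inconsistent.

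**There is no bias.** For the policy of starting at a level and applying the protocol's cuts, the count is unbiased, and expansion subjects would presumably be treated the same way. It understates the full three-dose DLT rate only if reduction lowers risk.

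A reader might infer that no rule at all covers subjects cut or stopped below a DLT. The clauses taken together do imply one. A reader might also infer that Sections 3.3 and 6.3.1 classify ordinary renal or hepatic stops differently. Their severe-event lists name neither kind of change, so this is not shown. The renal and hepatic conflict lies between the 3.3 hold-and-rechallenge provision and the 3.4 Grade 3 criterion.

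**Conclusion.** The DLT definition and the cut, hold and stop triggers are inconsistent as written across Sections 3.1, 3.3, 3.4 and 6.3.1, and they should be reconciled. The consequence is discrete: under a fewer-than-2-of-6 rule, one event read differently can decide a level. This part rests on the text alone.

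The counting of reduced or stopped subjects is settled by implication and needs only confirming. At Level 2 such a subject may have received 330, 300, 210 or 120 of 360 mg/m². A reader might infer that the MTD is biased upward by a known amount. The documents do not support that: they give no DLT rate, no share reduced and no effect of reduction on risk. The illustrative shifts run from zero to about 12 points (31% to 43%), and the larger ones need a third of subjects reduced and their whole-course risk halved although dose 1 was given in full. Dosing is also capped at 120 mg/m²/day, below the 150 mg/m²/day MTD of the earlier ALL study (a different population), so the lower risks may apply.

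**What to change.** 1. Reconcile Sections 3.1, 3.3, 3.4 and 6.3.1, and the matching synopsis text, so that one DLT definition and one set of cut, hold and stop triggers apply throughout. Which clinical rule is adopted is for the sponsor and its clinical advisers; none is proposed here.
2. Confirm the implied count in 4.3.2: subjects cut or stopped for toxicity below a DLT stay at the assigned level as non-DLTs and are not replaced by default. Replacement can itself distort the rate. Assume 20% of subjects carry a risk of 0.55, the rest 0.275, and the high-risk subjects are the ones stopped. Overall risk is 0.8 × 0.275 + 0.2 × 0.55 = 0.33, which clears with probability 43%. Replacing the high-risk subjects leaves 0.275, which clears with probability 55%.
3. At each escalation and MTD/RP2D decision, give the SRC the DLTs tabulated by dose actually received. Keep this descriptive. A second 3+3 count without these subjects could leave 0/2 or 1/2, for which the design has no decision.

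The cost is protocol wording and one extra table per decision, with no added subjects. The downside is that the table may make the MTD look less clear-cut.

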5. STUDY TREATMENT

5.1 Liposomal Annamycin (Study Drug)

5.1.1 Description of Liposomal Annamycin

Annamycin is a lipophilic anthracycline antibiotic that incorporates 4 structural modifications from doxorubicin: 2'-iodo, 3'-hydroxy, 4'-epi, 4-demethoxy doxorubicin. Annamycin is completely insoluble in water but soluble in chloroform and dimethyl sulfoxide.

Liposomal annamycin will be supplied by Moleculin Biotech, Inc., in 50-mL vials containing annamycin as a lyophilized powder. The study drug also contains phospholipids (dimyristoylphosphatidyl choline and dimyristoylphosphatidyl glycerol) and polysorbate 20.

Study drug will be shipped to the pharmacy at the study site in individually labeled vials. Each vial is labeled with the following information: drug name, strength, lot number, date of manufacture, storage conditions, sponsor's address, manufacturer's name, and the statement "Caution: New Drug - Limited to Investigational Use."

This study is an open-label study, and study drug will not be blinded, nor will placebo product be administered.

5.1.2 Preparation of Liposomal Annamycin

The study drug must be reconstituted prior to use. The diluted product can be held for up to 24 hours when stored between 34 to 42°C, after which time unused drug should not be administered to subjects.

Caution should be exercised in the handling and preparation of liposomal annamycin. The use of gloves is required. If liposomal annamycin comes into contact with skin or mucosa, immediately wash thoroughly with soap and water. Liposomal annamycin should be handled in a manner consistent with other anticancer drugs.

5.1.3 Liposomal Annamycin Administration

Subjects will be treated daily for 3 consecutive days with a 2-hour intravenous infusion of liposomal annamycin followed by 18 days off liposomal annamycin (i.e., 1 treatment cycle = 21 days). A peripheral vein may be used. The starting dose of liposomal annamycin (dose for subjects in Cohort 1) is 100 mg/m²/day. The liposomal annamycin doses will be escalated in sequential cohorts. Discussions of dose escalation and modifications are provided in [Section 3.2](#) and [Table 3](#).

5.1.4 Storage

At the study site, all investigational study drugs will be stored in a locked, safe area to prevent unauthorized access. The lyophilized liposomal annamycin powder should be stored in the

freezer at -10 to -25°C (-13 to 14°F). The reconstituted liposomal annamycin suspension is prepared as described in the Pharmacy Manual.

5.2 Concomitant Medications

All medications, whether prescription or nonprescription and including pharmacologic doses of vitamins, must be recorded on the Electronic Case Report Form/Electronic Data Capture (eCRF/EDC).

Subjects must not be receiving chemotherapeutics that are or may be active against AML, including investigational agents, while taking study drug, except for prophylaxis and/or treatment of opportunistic or other infection with antibiotics, antifungals, and/or antiviral agents. Subjects should not be undergoing concurrent radiation therapy. No new investigational treatments are to be initiated during the subject's participation in the study.

On the basis of the known metabolism of anthracyclines by CYP3A and CYP2B, enzymes of the Cytochrome P450 family, strong inducers and inhibitors of these enzymes will be prohibited during the days of treatment. Information about relevant drugs can be accessed through this website: <http://bioinformatics.charite.de/transformer/>, which easily provides drug interaction information; however, any concerns should be discussed with the Sponsor.

